4.3 Inclusion criteria

In order to be eligible to participate in this study, a subject must meet all of the following criteria:

1. Acute myocardial infarction, STEMI or NSTEMI
2. Cardiogenic shock, characterized by:
 - I. Signs of impaired organ perfusion with at least one of the following criteria:
 - a. Altered mental status
 - b. Cold, clammy skin and extremities
 - c. Oliguria with urine output < 30ml/hour
 - d. Serum lactate > 2.0 mmol/L
 - II.
 - a. Systolic blood pressure (SBP) < 90 mmHg for > 30 minutes, OR
 - b. Use of drugs to maintain SBP > 90 mmHg at presentation before randomization.
 - III. Signs of pulmonary congestion

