7.1.3 Laboratory data

The following laboratory data, that are part of routine care unless stated otherwise, are entered into the eCRF (*for details, see table 2*):

- Cardiac enzymes: serial measurements during the first 72 hours for hs-troponine T and CK-MB*.
- Lactate: will be measured at baseline, at 3 and 6 hours after randomization and with larger intervals hereafter.
- Creatinine: serial creatinine-levels during ICU / CCU stay, level at one year
- Other: C-reactive protein, glucose, hemoglobin, leukocytes, nt-proBNP* and blood urea nitrogen will be measured on admission and daily during ICU/CCU stay.

* Not part of routine care in every hospital

	T = 0 (ICU admission)	T = 3	T = 6	T = 12	T = 24	Day 2	Day 3	Day 4
Lactate	X	X	X	X	X	X	X	X
Hb	X				X	X	X	X
Leukocytes	X				X	X	X	X
CRP	X				X	X	X	X
Glucose	X							
Creatinin	X				X	X	X	X
Blood urea nitrogen	X				X	X	X	X
Liver function	X				X	X	X	X
Troponine T(hs)	X		X	X	X		X	
CK-MB	X		X	X	X		X	
Nt-proBNP	X					X		
Hourly blood pressure and heart rate for the first 24h	X	X	X	X	X			
Invasive haemodynamic measurements	X		X	X	X	X		
Urine production					X	X	X	X
Echocardiography							X	
ECG	X		X		X	X	X	X

Table 2.

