8.3 Tertiary endpoints *(for definitions, see Appendix A)*

The tertiary endpoints are:

- Days alive and out of ICU (30 days)
- Cardiovascular death at 1 year
- Enzymatic infarct size
- Lactate clearance (mean + area under the curve 0-36 hours)
- Days alive and free of mechanical ventilation (30 days)
- Days alive and free of mechanical circulatory support (30 days)
- Severe renal failure requiring renal replacement therapy (at 30 days, 1 year)
- Renal function (during hospital stay and 1 year)
- Time to peak creatinine (hospital stay)
- Time to renal replacement therapy
- Days alive and free of catecholamine therapy (30 days)
- Vasoactive inotropic score (VIS) (during hospital stay)
- Time to hemodynamic stabilization (hospital stay)
- Blood pressure and heart rate during the first 24 hours
- Hemodynamic parameters (during ICU / CCU admission)
- Arrhythmias during hospital admission
- Major vascular complication during admission (bleed or thrombo embolic event)
- Infection / sepsis during hospital admission
- Myocardial re-infarction within 30 days
- Left ventricular ejection fraction (at day 3, before hospital discharge, and at 1 year)

- Neurological outcome (at 30 days and 1 year)
- Protocol adherence / use of bail-out therapy
- Hospital readmission for cardiac reason within 1 year

The cost-effectiveness endpoints are:

- Health-related quality of life based on the EQ-5D-5L questionnaire at 12 months
- Resource utilization based on iMTA Medical Consumption (iMCQ) and iMTA Productivity Cost Questionnaire (iPCQ) (at 30-day, 3-month, 6-month and 1-year follow-up)

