11. ORGANIZATIONAL STRUCTURE

11.1 Clinical event committee

Clinical events that are part of the composite primary endpoint and the secondary endpoints are adjudicated by an independent clinical event committee (CEC). Members of the CEC are kept unaware of the regimen group assignments. If not stated otherwise, all analyses are based on findings as confirmed by the CEC.

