BARC 2	Any overt, actionable sign of hemorrhage (e.g., more bleeding than would be expected for a clinical circumstance, including bleeding found by imaging alone)

	that does not fit the criteria for type 3, 4, or 5 but does meet at least one of the following criteria: 
 • requiring nonsurgical, medical intervention by a health-care professional, • leading to hospitalization or increased level of care, or prompting evaluation
BARC 3	Clinical, laboratory and/or imaging evidence of bleeding with specific healthcare provider responses as listed below:
3a	
 • Overt bleeding plus hemoglobin drop of 3 to < 5 g/dL* (provided hemoglobin drop is related to bleed) • Any transfusion with overt bleeding
3b	
 • Overt bleeding plus hemoglobin drop ≥5 g/dL* (provided hemoglobin drop is related to bleed), • Cardiac tamponade • Bleeding requiring surgical intervention for control (excluding dental/nasal/skin/hemorrhoid) • Bleeding requiring intravenous vasoactive agents
3c	Intracranial hemorrhage (does not include microbleeds or hemorrhagic transformation, does include intraspinal)
BARC 4	CABG-related bleeding 
 • Perioperative intracranial bleeding within 48 h. • Reoperation after closure of sternotomy for the purpose of controlling bleeding • Transfusion of ≥ 5 U whole blood or packed red blood cells within a 48-h period • Chest tube output more than or equal to 2L within a 24-h period
BARC 5	Fatal bleeding
5a	Probable fatal bleeding; no autopsy or imaging confirmation but clinically suspicious
5b	Definite fatal bleeding; overt bleeding or autopsy or imaging confirmation

Infection / sepsis during admission

Culture proven or for which antibiotics have been started because of high suspicion.

Myocardial re-infarction within 30 days

Acute myocardial injury with clinical evidence of acute myocardial ischemia and with detection of a rise and/or fall of cardiac troponin values with at least one value above the 99th percentile upper reference limit and at least one of the following:

- Symptoms of myocardial ischemia
- New ischemic ECG changes
- Development of pathological Q waves
- Imaging evidence of new loss of viable myocardium or new regional wall motion abnormality in a pattern consistent with an ischemic etiology

Identification of a coronary thrombus by angiography or autopsy

Left ventricular ejection fraction

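### The definition of re-infarction within 30 days uses criteria for any acute infarction, so in the first days it does not separate a recurrence from the index event

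*Protocol*

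**What the plan says.** Section 8.3 lists "Myocardial re-infarction within 30 days" as a tertiary endpoint and refers to Appendix A for definitions. The Appendix A entry is the only definition of re-infarction in the protocol. It asks for "Acute myocardial injury with clinical evidence of acute myocardial ischemia and with detection of a rise and/or fall of cardiac troponin values". A single result over the 99th percentile is enough for the troponin part, and any one of five supporting items completes the definition:

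- "Symptoms of myocardial ischemia"
- new ischemic ECG changes
- development of pathological Q waves
- imaging evidence of new myocardial loss or a new wall-motion abnormality
- "Identification of a coronary thrombus by angiography or autopsy"

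The first inclusion criterion in section 4.3 is "Acute myocardial infarction, STEMI or NSTEMI". Section 5.1 places randomization before PCI or at most 2 hours after it. Section 7.1.3 schedules "serial measurements during the first 72 hours for hs-troponine T and CK-MB".

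On adjudication, section 11.1 opens with "Clinical events that are part of the composite primary endpoint and the secondary endpoints are adjudicated by an independent clinical event committee". It adds that members do not know the assignment. It closes by making committee-confirmed findings the default basis of every analysis, unless stated otherwise.

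**The concern.** The definition would suit a population without a recent infarction. Here every patient has one, and its biomarker curve runs on into follow-up. A rule for re-infarction in this setting has to say what sets the second event apart from the first, and this one does not.

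Recurrent infarction bears on the comparison. The rationale in section 1 concerns myocardial perfusion and expansion of infarct size, and the Summary attributes all potential risk to the lower MAP target and the reduced use of noradrenaline. If the criteria cannot tell early recurrence from index evolution, whoever classifies the event must do so by judgement. The trial is open label. Where that judgement is made by someone who knows the assignment, ascertainment could differ between arms. Where it is made blind, misclassification would more likely dilute any difference.

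**Working it through.** The protocol gives no figure for this endpoint, so there is nothing to reproduce. The check sets each element of the definition against what the index infarction already supplies.

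1. **Acute injury with clinical ischemia.** The entry criterion supplies this at presentation. The definition does not say that the ischemia must arise after randomization.
2. **Troponin rise and/or fall, one value above the 99th percentile.** Table 2 schedules hs-troponin T at T = 0, 6, 12 and 24 hours and on day 3. With randomization no later than 2 hours after PCI, these samples follow the index curve. Appendix A uses the same 72-hour series to measure enzymatic infarct size, so the plan itself treats that curve as a measure of the index infarct. A fall alone is enough, and no re-rise from a stable or falling value is required.
3. **One supporting item.** The symptom and thrombus items carry no qualifier tying them to a second event, so presenting symptoms or the culprit thrombus at index angiography can satisfy them. Q-wave development can be evolution of the index infarct on the scheduled ECGs (T = 0, 6 and 24 hours, days 2 to 4). The ECG and imaging items say new, but without a reference point.
4. **Exclusion of the index event.** None is stated here or elsewhere in the protocol. The lack of an anchor is particular to this entry: Appendix A counts time to renal replacement therapy from randomization, and counts readmission only after discharge from the initial hospitalization.
5. **Start of the window.** Sections 7.1.5 and 8.3 say within 30 days but name no starting point for this endpoint. Section 8.1 does so for the primary endpoint.

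No element fails for the index infarction, and no element separates it from an early recurrence.

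**Illustration with assumed rates (not in the protocol).** Section 9.3 gives 388 patients per arm. Suppose a true 30-day rate of 2% to 5%, and that 5% to 10% of the other patients are misclassified.

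- True events: 0.02 × 388 = 7.8 to 0.05 × 388 = 19.4.
- Other patients: 388 − 7.8 = 380.2 to 388 − 19.4 = 368.6.
- False events: 0.05 × 368.6 = 18.4 to 0.10 × 380.2 = 38.0.

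At 5% true and 5% false, the counts are 19.4 and 18.4, so false events do not always outnumber true ones. The calculation shows only that modest misclassification could be of the same order as a low true rate.

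**The case against.** The strongest reply is that the heading says re-infarction, two items say new and a third speaks of development. A sensible reader would not code the entry infarct as its own recurrence. That stands as to intent. It supplies no operating criterion for the early days, when a reader who accepts the intent still has no rule for telling the two apart.

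It is also fair that falling troponin with evolving Q waves does not by itself meet the text, because clinical evidence of acute ischemia is required as well. The gap is that this evidence is not tied to a time after the index event, so the presenting ischemia is not ruled out.

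On adjudication, a reader might infer from the opening of section 11.1 that unblinded sites alone classify this tertiary endpoint. The documents do not settle that. The closing sentence of the section points towards committee confirmation. The protocol also uses the word secondary loosely: the Summary calls enzymatic infarct size and hemodynamic parameters secondary, while section 8.3 lists them as tertiary. Committee review is therefore unclear, but not ruled out. A committee applying the present text would face the same gap.

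The statistical analysis plan might add a rule. However, the protocol fixes this definition itself, so the matter is not one simply left to that plan.

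**Conclusion.** The point holds for early events. While the index troponin is still moving, the written criteria can be met by the index infarction and do not distinguish it from a true recurrence. A late event, after troponin has settled, is easier to recognize clinically, although the definition gives no rule for it either.

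A reader might go further and infer that nearly every patient would be counted, so that the rate approaches 100% in both arms. That follows only from a literal reading that ignores the heading and the word new. It is not a forecast that the documents support. The size of any misclassification is unknown.

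The consequence is limited. This is one tertiary endpoint. It does not enter the primary composite, the hierarchical tests in section 9.2 or the sample size in section 9.3. The stopping guidance in section 9.7 names only the primary endpoint and all-cause death. The conclusion rests on the Appendix A entry being the operative definition.

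**What to change.** In Appendix A:

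- Require an event after randomization that is distinct from the index infarction.
- Require new ischemic evidence (symptoms, ECG change or angiographic finding) together with a renewed rise of troponin or CK-MB from a stable or falling value. The sponsor should choose the size of that rise and prespecify it.
- State that falling index troponin, evolving Q waves, the index culprit thrombus and the index wall-motion abnormality do not count.

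In section 11.1, state that the existing blinded committee adjudicates suspected re-infarctions.

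The change needs only wording and a few more cases for the committee. It has two limits. Very early recurrences, before the biomarker peak, may be missed. After day 3 the re-rise rule depends on clinically triggered samples, because scheduled troponin and CK-MB end then, and section 7.1.3 notes that CK-MB is not routine in every hospital.
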